### 2.2 Secondary Objectives

The secondary objectives are to compare the treatment groups for the following outcomes:

- Cumulative response – The cumulative response rate from Week 6 to Week 25 of treatment. Response is defined as the presence of both a negative urine drug test for opioids and a negative self-report for illicit use of opioids at a study visit.
- Illicit use of opioids - The cumulative response rate from Week 6 to Week 25 of treatment with respect to the percentage of urine drug tests negative for opioids.
- Self-report of illicit use of opioids - The cumulative response rate from Week 6 to Week 25 of treatment with respect to the percentage of negative self-reports for illicit use of opioids.
- Percentage of subjects abstinent - Abstinence is defined as a subject having a urine drug test negative for opioids as well as negative self-reports for illicit use of opioids at Week 25.
- Proportion of subjects completing the study - A completer is defined as a participant who completed either the UDS or the self-report assessment at the Week 25 visit.
- Clinical global impression - Will be evaluated by:
  - Score on the Clinical Global Impression-Improvement (CGI-I) scale at Week 12 and Week 25
  - Change from baseline in the Clinical Global Impression-Severity (CGI-S) score at Week 12 and Week 25

- Opioid cravings - Change from baseline in the opioid craving score using the opioid craving visual analog scale (VAS) from Week 4 to Week 25.
- Use of illicit non-opioid drugs of abuse - The cumulative percentage of subjects with urine drug tests negative for illicit drugs of abuse (excluding opioids) plus negative self-reports for illicit drug use from Week 6 to Week 25.
- Number of hospitalizations, emergency department visits, and overdoses, and the ability to resume work, school, or other productive activity.
- Adverse events (AE)

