CGI scores will be evaluated using general linear model methodology or non-parametric analogs.

- Opioid cravings - Change from baseline in the opioid craving score using the Opioid Craving VAS from Week 4 to Week 25. Opioid Craving scores will be evaluated using general linear model methodology or non-parametric analogs.
- Use of illicit non-opioid drugs of abuse - The cumulative percentage of subjects with urine drug tests negative for illicit drugs of abuse (excluding opioids) plus self-reports negative for illicit drug use for the period from Week 6 to Week 25 will be evaluated using the Kolmogorov-Smirnoff methodology.

- Number of hospitalizations, emergency department visits, and overdoses, and the ability to resume work, school, or other productive activity.

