**✓ WHAT TO FILL IN**

- The idea is that for **each day** on the calendar we want you to indicate whether you "used" or "did not use" drugs. Specifically indicate whether you have used any of the following: amphetamines (uppers), barbiturates, benzodiazepines (for example, Xanax, Ativan, Valium), cocaine, marijuana, methadone, opiates (for example, oxycodone, hydrocodone), phencyclidine (PCP).
- On days when you **did not use drugs**, you should write a "0" in the box.
- On days when you **did use drugs**, you should put a "✓" in the box.

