2 STUDY OVERVIEW

2.1 Study Objectives and Endpoints

2.1.1 *Primary Objective and endpoint*

The primary objective of the study is to determine whether the combination of sublingual (SL) buprenorphine/naloxone (BUP/NAL) standard of care (SOC) background therapy and the digital therapeutic OXD01 is superior to SL BUP/NAL alone to reduce opioid use, as measured by the treatment success rate. Treatment success is defined as the subject having $\geq 80\%$ of urine drug tests negative for opioids plus negative self-reports for illicit opioid use (from the timeline followback (TLFB) interview at the same visit) from Week 6 to Week 25.

2.1.2 *Secondary Objectives and Endpoints*

Compare the treatment groups for the following outcomes:

- Cumulative response – The cumulative response rate over a period from Week 6 to Week 25 of treatment. Response is defined as the presence of both a negative urine drug test for opioids and a self-report negative for illicit use of opioids at a study visit.
- Illicit opioid use - The cumulative response rate over a period from Week 6 to Week 25 of treatment with respect to the percentage of urine drug tests negative for opioids.
- Self-reports of illicit opioid use - The cumulative response rate over a period from Week 6 to Week 25 of treatment with respect to the percentage of self-reports negative for illicit opioid use.
- Percentage of subjects abstinent - Abstinence is defined as a subject having a urine drug test negative for opioids as well as self-reports negative for illicit opioid use at Week 25.
- Proportion of subjects completing the study - A completer is defined as a participant who completed either the urine drug screen (UDS) or the self-report assessment at the Week 25 visit.
- Clinical global impression - This will be evaluated in two ways:
 - Score on the Clinical Global Impression-Improvement scale at Week 13 and Week 25
 - Change from baseline in the Clinical Global Impression-Severity score at Week 13 and Week 25
- Opioid cravings - Change from baseline in the opioid craving score using the Opioid Craving Visual Analog Scale from Week 4 to Week 25.
- Illicit use of non-opioid drugs of abuse - The cumulative percentage of subjects with urine drug tests negative for drugs of abuse (excluding opioids) plus self-reports negative for use of drugs of abuse for the period from Week 6 to Week 25.

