3.4 Efficacy Assessment

Efficacy data will be summarized by randomized treatment based on the FA Population. The primary efficacy endpoint will also be summarized based on the mFA Population.

3.4.1 *Primary Endpoints Analysis*

The primary objective of the study is to determine whether the combination of SL BUP/NAL SOC background therapy and the digital therapeutic OXD01 is superior to SL BUP/NAL alone to reduce opioid use, as measured by the treatment success rate. Treatment success is defined as the subject having $\geq 80\%$ of urine drug tests negative for opioids plus $\geq 80\%$ of self-reports negative for illicit opioid use (from the TLFB interview at the same visit) from Week 6 to Week 25. Each subject will be evaluated as a success or failure for this metric and the proportion of subjects in each group demonstrating $\geq 80\%$ of urine drug tests negative for opioids plus negative self-reports for illicit opioid use (from the TLFB interview) will be tested using chi-squared test. Count and percentage of the subjects with treatment success will be summarized by treatment based on FA Population.

If the subject withdrew the study, then the urine drug tests for opioids and self-reports for illicit opioid use after withdrawal will be imputed as positive. If the subject completed the study with any missing visit, then the urine drug tests for opioids and self-reports for illicit opioid use for the missing visit will be imputed as positive.

Sensitivity analysis 1

As supportive analyses to the primary analysis for the primary endpoint, sub-group analysis using a similar chi-squared test as described above will be repeated for the following factors:

- Percentage of subjects meeting primary endpoint by reported compliance rate or who achieved greater than 80% completion of the visits during Week 6 to Week 25
- Subjects who took the dose of buprenorphine versus retention.
 - Target dose or lower: ≤ 16 mg buprenorphine for Suboxone or equivalent formulation; or ≤ 11.4 mg Zubsolv
 - Higher dose than target dose: > 16 mg buprenorphine for Suboxone or equivalent formulation; or > 11.4 mg Zubsolv
- Subjects who received additional behavioral health services

Sensitivity analysis 2

As supportive analyses, the primary endpoint and key secondary endpoints will be performed using the similar statistical methods based on mFA Population.

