- Proportion of subjects completing the study - A completer is defined as a participant who completed either the UDS or the self-report assessment at the Week 25 visit. The groups will be compared with respect to the proportion of completers using a chi-squared test.
- Clinical global impression - This will be evaluated in two ways
 - Score on the CGI-I scale at week 13 and Week 25
 - Change from baseline in the Clinical Global Impression-Severity score at Week 13 and Week 25

CGI scores will be evaluated using General Linear Model (GLM) methodology with treatment as categorical covariate. If substantial deviations from the model assumptions are observed, then supportive analyses such as non-parametric assessments including a Mann-Whitney U test will be performed.

- Opioid cravings - Change from baseline in the opioid craving score using the Opioid Craving VAS from Week 4 to Week 25. Opioid Craving scores will be evaluated using GLM methodology with treatment as categorical covariate. If substantial deviations from the model assumptions are observed, then supportive analyses such as non-parametric assessments including a Mann-Whitney U test will be performed.
- Use of illicit non-opioid drugs of abuse - The cumulative percentage of subjects with urine drug tests negative for illicit drugs of abuse (excluding opioids) plus self-reports negative for illicit drug use for the period from Week 6 to Week 25 will be evaluated using the Kolmogorov-Smirnoff methodology.
- Number of hospitalizations, emergency department visits, and overdoses, and the ability to resume work, school, or other productive activity. descriptive statistics (count and percentage) will be summarized by treatment.

3.4.3 *Exploratory Analysis*

- Percentage of subjects with longer abstinent – Longer abstinence is defined as a subject having urine drug tests negative for opioids as well as self-reports negative for illicit use of opioids at Week 22 – Week 25. Each subject will be scored as abstinent or non-abstinent and the groups will be compared using a chi-squared test.

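### The non-opioid drug endpoint excludes opioids from the urine part only, so an opioid-only self-report counts as non-opioid drug use

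*SAP*

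**What the plan says.** SAP 3.4.2 names the endpoint "Use of illicit non-opioid drugs of abuse" and defines it through "urine drug tests negative for illicit drugs of abuse (excluding opioids) plus self-reports negative for illicit drug use", cumulated over Week 6 to Week 25 and compared by the Kolmogorov-Smirnov method. SAP 2.1.2 has "urine drug tests negative for drugs of abuse (excluding opioids) plus self-reports negative for use of drugs of abuse". Protocol 2.2 has "urine drug tests negative for illicit drugs of abuse (excluding opioids) plus negative self-reports for illicit drug use". The protocol synopsis and Protocol 11.4 follow the same pattern.

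The self-report comes from the timeline followback (TLFB). Appendix E of the protocol gives one list of drugs for the calendar, which reads in part "marijuana, methadone, opiates (for example, oxycodone, hydrocodone), phencyclidine (PCP". Its sample calendar shows a single Drugs box per day, and Protocol 6.11 calls the instrument a closed yes/no question.

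Under SAP 3.4.2 the secondary endpoints are tested in a fixed order, each only if the one before it is significant. This endpoint follows cumulative response, opioid urine, opioid self-report, abstinence, completion, clinical global impression and craving. It is the last one with a test.

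The only imputation rule is in SAP 3.4.1, under the primary endpoint. For a subject who withdraws, "then the urine drug tests for opioids and self-reports for illicit opioid use after withdrawal will be imputed as positive"; missed visits of completers are treated likewise. It names opioid tests and opioid self-reports only.

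**The concern.** The label says non-opioid, but the definition carries that restriction into only one of its two components. Elsewhere the plan names opioids when it means opioid self-reports, so an unrestricted reference to illicit drug use reads as all drugs on the TLFB list, methadone and opiates included. Someone programming from the definition would fail a visit on an opioid report alone.

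The contamination is greatest when the test is formally run. By then an arm difference in opioid self-report has already been declared significant, and counting the same reports again can show that difference under a non-opioid label. The trial is open-label (Protocol 3.1.1), so self-report is also the component most exposed to a reporting difference between arms.

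A second gap sits alongside this. The SAP gives neither a denominator nor a missed-visit rule for the endpoint, although Protocol 11 says the SAP will contain the missing-data procedure.

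**Working it through.** **1. Wording.**

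| Place | Urine part | Self-report part |
|---|---|---|
| Protocol synopsis | opioids excluded | drugs of abuse, no exclusion |
| Protocol 2.2 | opioids excluded | illicit drug use, no exclusion |
| Protocol 11.4 | opioids excluded | illicit drug use, no exclusion |
| SAP 2.1.2 | opioids excluded | drugs of abuse, no exclusion |
| SAP 3.4.2 | opioids excluded | illicit drug use, no exclusion |

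The asymmetry is the same in all five.

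**2. One subject.** Weekly visits from Week 6 to Week 25 give 25 − 6 + 1 = 20. Take a subject who attends all 20, never uses a non-opioid drug, and reports opioid use at half of them. As written the score is 10/20 = 50%; with opioids excluded from both parts it is 20/20 = 100%. If opioid use is reported at 35% of visits, the scores are 13/20 = 65% and 100%.

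**3. Group means.** The documents give no figures for this endpoint, so these inputs are assumptions: non-opioid use at 20% of visits in both arms (no true effect), and opioid use, independent of it and always reported, at 50% of visits on control and 35% on OXD01. Expected proportion of negative visits among those attended:
- As written: 0.80 × 0.50 = 0.40 on control and 0.80 × 0.65 = 0.52 on OXD01, an apparent gain of 0.12.
- Opioids excluded from both parts: 0.80 and 0.80, a gain of 0.

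**4. Simulation of the single test.** 200 per arm, 1,000 runs, two-sided 0.05, large-sample Kolmogorov-Smirnov, between-subject variation by beta distributions, dropout unrelated to use. Percentage of runs rejecting, with no true non-opioid difference in any row:

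| Dropout, control / OXD01 | Opioid use, control / OXD01 | Excluded, attended visits | Excluded, missing = positive | Counted, attended visits | Counted, missing = positive |
|---|---|---|---|---|---|
| 40% / 40% | 50% / 50% | 2.7 | 3.5 | 3.5 | 1.9 |
| 40% / 40% | 50% / 35% | 2.6 | 2.8 | 84.9 | 68.0 |
| 50% / 35% | 50% / 50% | 2.3 | 33.6 | 3.7 | 7.5 |
| 50% / 35% | 50% / 35% | 3.1 | 33.9 | 86.3 | 94.4 |

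Rows 1 and 2 isolate the definition: counting opioid reports does no harm when the arms have the same opioid use and dominates when they differ. The size depends on the inputs. With a smaller contrast (opioid-negative self-report 50% against 60%, 3% weekly dropout in both arms), separate runs gave 22% to 26% with missing visits positive and 44% to 45% on attended visits, against about 3% with opioids excluded.

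**5. Effect of the fixed order.** Completion is tested before this endpoint. With equal true dropout (row 2) it is significant in only about 5% of trials, so the chance of reaching this endpoint and falsely rejecting is at most about 5%. Where retention truly differs, as in row 4 (completion 50% against 65%), the pooled rate is 0.575 and the completion test alone has z = [0.15 − 1.96 × √(2 × 0.575 × 0.425/200)] / √(0.50 × 0.50/200 + 0.65 × 0.35/200) = (0.15 − 0.0969)/0.0489 = 1.09, a power of about 86%. The remaining tests would still have to be passed.

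**6. Missed visits.** A subject with clean visits who leaves after 5, 10 or 15 of the 20 scores 100% on attended visits, but 5/20 = 25%, 10/20 = 50% or 15/20 = 75% if missing visits count as positive. Row 3 shows the cost of the latter: a pure retention difference produces rejection in 33.6% of runs, against 2.3% on attended visits.

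**7. Sample size.** For 12% against 25% at 90% power, n = [1.960 × √(2 × 0.185 × 0.815) + 1.282 × √(0.12 × 0.88 + 0.25 × 0.75)]² / 0.13² = 186 per arm, or 201 with continuity correction. Exact Fisher power at 200 per arm is 90.4%. The stated 200 reproduces and uses nothing from this endpoint.

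**The case against.** The best defence is that the label governs. The endpoint is about non-opioid drugs, so a sensible programmer would leave opioid reports out. The primary endpoint already needs opioid self-reports identified separately, so the data should allow it. The endpoint is also last among the tested ones and will often not be reached. Much of this is fair. The label does show intent, but that makes the definition wrong rather than clear, because the definition is what gets coded. The late position limits how often the result is claimed; it does not protect the result once the opioid self-report test has been passed.

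Four stronger inferences are tempting, and the documents do not support them.

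- That dropouts are scored on attended visits only, so that one clean visit yields 100%. The SAP gives no denominator, so this is one possible default. If opioid reports do count here and the SAP 3.4.1 rule carries over to secondary endpoints, a missed visit already fails through its imputed-positive opioid report.
- That missing = positive is the needed correction. It is a trade-off, and it can turn better retention into apparent drug abstinence.
- That the simulated percentages are the trial's false-positive rate. They describe one test on its own under assumed inputs.
- That the TLFB cannot separate drug classes. The printed sample has one box per day, but the instructions ask which drugs were used and the case report form is not shown. The point needs confirming and is not established.

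**Conclusion.** The point holds for the definition. In both documents, an opioid-only self-report makes a visit positive on an endpoint labelled non-opioid. If the arms differ in opioid use or in its reporting, the endpoint can show a benefit that does not exist. The illustrative distortion is 0.12 in the mean proportion of negative visits, with the single test rejecting in 68% to 85% of runs against about 3%. This rests on assumed use rates, independence of opioid and non-opioid use, full reporting, and dropout unrelated to use. The rate under the full hierarchy is lower and cannot be fixed from the documents.

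On missing data the finding is silence: the SAP should state a rule, and neither option is shown to be the right one. The primary analysis, the sample size and the opioid endpoints are untouched. This should be corrected, but it does not threaten the trial's main conclusion.

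**What to change.** Define a negative visit as urine negative for the non-opioid panel drugs together with a self-report negative for non-opioid drugs. Put the opioid exclusion on both parts in SAP 2.1.2 and 3.4.2 and in the protocol synopsis, 2.2 and 11.4. Name the drug classes that count, leaving out the opioid items of the Protocol 6.9 panel (methadone, opiates, propoxyphene, buprenorphine).

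Confirm that the collected TLFB data separate opioid from non-opioid use. If they do, the change costs a few words and a small change to the derivation. If they do not, the self-report part cannot be derived as intended. The SAP should then say so and say what the endpoint will rest on.

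State the denominator and the handling of missed visits, post-withdrawal visits and subjects with no visit in the window. Give the reason for the choice and report the alternative as a sensitivity analysis, with retention shown by arm next to it. This costs one paragraph and one extra table, and should be settled before database lock.

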3.5 Safety Assessment

Safety data will be summarized by actual treatment received based on the Safety Population.

3.5.1 *Adverse Events (AEs)*

An adverse event is any untoward medical occurrence in a subject or clinical trial subject caused by, or associated with a device and which does not necessarily have to have a causal

relationship with the device. An AE can therefore be any unfavorable and unintended sign, symptom, or disease temporally associated with the use of the device, whether or not considered related to the intended use of the device.

Pre-existing conditions will not be regarded as AEs if the condition follows a normal course of recovery, unless it worsens after exposure to the device. Medical procedures will not be regarded as AEs, but the cause of the procedure may be.

The AE reporting period will start after signing the informed consent form and will end at discharge from the study. All AEs will be coded to system organ class and preferred term using MedDRA version 24.0.

Adverse events with missing start dates will be considered as device related AE unless the partial date excludes that possibility. Otherwise, the first day of the month will be used to impute missing start days and January will be used to impute missing start months. If the causality for an adverse event is missing, the adverse event will be assumed to be related.

A Serious Adverse Event (SAE) is an AE that:

- results in death
- is life threatening
- requires hospitalization or prolongation of existing hospitalization
- results in persistent or significant disability/incapacity
- is a congenital anomaly/birth defect
- is another important medical event (e.g., convulsions not leading to hospitalization)

SAEs will only be considered when there is an underlying AE. For example, a hospitalization due to a pre-existing condition which is not due to an aggravation of the condition after exposure to any study treatment will not be considered to be an SAE.

An unanticipated adverse device effect (UADE) is any serious adverse effect on health or safety, any life threatening problem or death caused by, or associated with a device, if that effect, problem, or death was not previously identified in nature, severity, or degree of incidence in the device; or any other unanticipated serious problem associated with a device that relates to the safety or welfare of subjects.

The Quantity-Frequency Index (QFI) is a self-assessment of the frequency and quantity of alcohol consumption over the previous 30 days. The QFI is comprised of the two questions and will be completed on study Day 1 and at the visit on Week 25.

Individual data listings of QFI will be presented for each subject and visit of collection.

3.5.6 *Timeline Followback Method – Drug and Alcohol Use*

The Timeline Followback Method – Drug and Alcohol Use (TLFB) is a self-assessment used to document recent use of opioids, other illicit drugs of abuse, and alcohol. A TLFB assessment will be completed on study Day 1, and at weekly visits while on study treatment. The TLFB is a closed Yes or No question of drug or alcohol use.

Individual data listings of TLFB – drugs and TLFB – alcohol will be presented for each subject and visit of collection, separately.

3.5.7 *Opioid Craving Visual Analog Scale*

Cravings for opioids will be assessed by the subject through the use of a VAS, where 0 mm represents “no cravings” and 100 mm represents “the most intensive craving I have ever had.” The baseline craving VAS assessment will be collected on study Day 1 and at the visit on Weeks 5, 9, 13, 17, 21 and 25.

Individual data listings of opioid craving VAS will be presented for each subject and visit of collection.

3.5.8 *Quick Inventory of Depression Symptoms (Self-Report)*

Symptoms of depression will be assessed by the subject using the Quick Inventory of Depression Symptoms Self-Report (QIDS-SR) at screening and at the visit on Week 25.

Individual data listings of QIDS-SR will be presented for each subject and visit of collection.

3.5.9 *Review Behavioral Health Therapies since The Previous Visit*

Subjects in behavioral health therapies since the previous visit, including 12-step programs, will be recorded at the visits on Weeks 1-5, 7, 9, 11, 13, 17, and 21 in eCRF.

Individual data listings of behavioral health since previous visit will be presented for each subject and visit of collection.

3.5.10 *Clinical Global Impression*

Clinical Global Impression (Severity) – Severity of opioid dependence will be assessed by the Investigator on study Day 1 and at the visit on Week 13 and Week 25 using the assessment scale (rate from 0 to 7).

Clinical Global Impression (Improvement) – Improvement in severity of opioid dependence from baseline (study Day 1) will be assessed by the Investigator at the visit on Week 13 and Week 25 using the assessment scale (rate from 0 to 7).

Individual data listings of Clinical Global Impression severity/ improvement (CGI-S/I) will be presented for each subject and visit of collection.

